Group 2 (or experimental EmoLED protocol group) will be visited once a week. Therapy in this case includes, in addition to the standard therapy, a treatment with EmoLED device; it consists in irradiating each 5 cm diameter area of the lesion for 60 seconds, with the blue light emitted by the device. For lesions larger than 5 cm, several applications will be applied on adjacent areas, until the whole lesion is covered.

EmoLED is a medical device for light therapy (Class IIa), portable and battery-powered. Its intended use is the care of acute and chronic skin lesions by healthcare staff on patients over 16 years old, regardless of their ethnicity. Related adverse events, incidents or side effects haven't been observed during previous clinical trials and clinical experiences; therefore, no risks are reported in addition to the ones related to the use of light in medicine. However, the device is labelled and written instructions are provided for a safe use.

The objective of the study is to assess eventual differences in the outcome between the two groups and to determine if the therapy of Group 2 is a valid alternative to the standard therapy in terms of healing rate, quality of life and economic impact:

- The primary endpoint of the study is the percentage/rate of lesion area reduction
- The secondary endpoints are, together with other clinical parameters aimed at evaluating the general clinical situation, quality of life and costs related to the two treatments.

There is a follow-up after 4 weeks since the end of the period of observation (it may end at the 16th week or earlier).

Ethical considerations

The study will be submitted to the Ethical Committee of each investigator hospital for approval and in any case will be performed according to the GCP, the Helsinki Declaration and the Italian laws and requirements in the matter of human clinical trials.

L.U.C.E. Study Protocol version 3.0 (24/02/2020)

10

Informed consent procedure

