The parameters of the Data Collection Form are acquired and kept on paper for the clinical trial lenght, and conserved in both paper and digital form; the pictures of the lesion are acquired and kept in digital form, during the length of the clinical trial and afterwards.

During each visit, a picture of the lesion will be taken so that the process of healing can be valued also in a visual way. Each picture will be named with the patient code and the date of the visit. In case of multiple lesions matching with both inclusion and exclusion criteria, they will be all treated following the same protocol, depending on the group of treatment, but only the lesion with the wider area will be registered; to distinguish the area of interest, the perilesional tissue will be labelled with single-use permanent markers.

Data Collection Form

The Data Collection Form is unique for each patient and includes: Clinical Section, Quality Life Section and Economic Section. The Clinical Section contains identification code of the patient, date of birth, sex, etiology of the ulcer, any eventual concurrent disease, any drug therapy (in terms of active substances), ulcer's date of onset, date of entry to the facility.

The second part of the form is organized as a matrix where the row represents the measurable parameters for each time of observation (reported in column).

The investigator marks with an "X" the chosen value for each parameter and the most suitable description. The Principal Investigator will also fill a check list, for each visit, to ensure that also the pain level has been measured and that the picture of the lesion has been taken.

There is also a "Notes" section to register information not planned at first, that might be helpful during the data analysis.

The last part of the Data Collection Form is about follow-up visit (after 4 weeks).

The Data Collection Form is already completed with the patient's recruitment code and the group they belong to, so that the allocation to the EmoLED group and the control group is random. The allocation sequence of the group is generated by Matlab.

On each visit, the patient will be asked to rate their current pain level (VAS scale 0-10).

The quality section survey will be administered on the first and last visits, and also every 4 weeks. In detail, standard questionnaires as the EQ-5D2 and the Wound-Qol3 will be administered, both available and validated in Italian language.

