Specific questionnaires for recognition of costs (Economic section) will be administered to patients and their primary caregiver (if present) during the first visit, with the aim of identifying the resources absorbed by the patients (and their caregivers) treated in the two different approaches. The consumption of resources will be measured by gathering information about the quantification of direct health costs (visits, hospitalizations, emergency healthcare, medications etc...), direct non-health-related costs (informal medical assistance, transportation and accommodation costs for each visit etc...) and indirect costs (productivity loss for both the patient and the caregiver/s) and also by taking into account both the costs associated with the adherence to the treatment, taking the first visit as a reference parameter, and the costs related to complications and events associated with the ulcer that determined the need for treatments/ exams and/or medical evaluations. The Principal Investigator will be given also a questionnaire to determine the costs incurred by their facility for handling patients with leg ulcers.

The questionnaires meant to value customer satisfaction, complexity and helpfulness of EmoLED device will be administered to doctors and to healthcare personnel involved in the treatment at the end of the trial.

Image Acquisition

For the 16 weeks of the trial, during each visit a picture of the lesion will be taken, so that the process of healing can be valued also in a visual way. Each picture will be named with the patient code and the date of the visit. The quantitative analysis about the size of the lesions through the collected pictures will be performed at certain time points: at the beginning, in the middle and at the end of the treatment.

The image analysis is made through an appropriate analysis algorithm that measures the area of the lesion (mm²). The lesion must be fully and frontally framed to obtain an optimal analysis. The ruler with patient's ID code and date must appear in every picture. It is important that the ruler is placed straight and in-focus to have the scale reference. If there is a wide lesion that needs more than one picture it's advisable to

L.U.C.E. Study Protocol version 3.0 (24/02/2020)

locate several markers around the lesion and take photos of adjacent areas, including at least two visible markers of the previous picture, to have the complete image of the lesion through a sequential photo array.

Bias

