The staff participating in the study is trained on the correct use of the device and accessories, as well as on the correct execution of the clinical protocol and on the compilation of the related forms. In any case, the EMOLED staff is always available to the team for any clarification or doubt during the study. In order to promote a more homogeneous operation between the various centres, joint training sessions are organized and documents which serve as guidelines for the most critical passages or the ones which require particular attention, such as recording, saving and transmitting data, are prepared. In order to avoid bias during the procedure of allocation in groups of patients enrolled in the study, it should be noted that the randomization grid is not distributed to the investigators: instead, paper folders are distributed containing the data collection forms. The progressive patient ID is on the outside of the folders, while on the inside a label is placed with the assignment of the patient to one of the two groups (Control or EmoLED treatment), which reflects the randomization grid. These folders are closed through an adhesive label with the signature of the Head of Clinical Affairs of the sponsoring company.

Patients selection

All patients that satisfy all the inclusion criteria, both hospitalised and outpatient, will be considered for inclusion in this study.

It will be used a standard procedure to value patients that includes the anamnesis evaluation and a physical examination.

Inclusion criteria

- Subjects suffering from venous and mixed skin ulcers;
- Presence of a lesion < 100 cm² of area and < 1 cm in depth;
- Men and women ≥ 18 years old;
- The patient must be able to understand the aims of the clinical trial and provide informed consent in writing;
- Chronicity of the lesion: at least 8 weeks.

Exclusion criteria

- Patients who participated in clinical trials about skin ulcers healing during the previous month;
- Patients who are not able to understand the aims of the trial;
- Patients with pressure ulcers;
- Patients with diabetic foot ulcers;
- Patients with circumferential leg ulcer (due to the difficulties in analysing the pictures);
- Patients with clearly infected ulcers or with systemic infection;
- Patients with ulcers caused by critical ischemia;
- Patients with a self-harm past that can purposely alter the process of healing;
- Patients with psychiatric disorders;

L.U.C.E. Study Protocol version 3.0 (24/02/2020)

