Known or predictable factors that may impair outcomes and interpretation of outcomes

A different therapy standard between participating centers and/or within the same center can lead to very variable outcomes between one patient and another, all other conditions being equal. This problem is tackled by indicating in detail the therapy to be followed depending on the type of lesion.

An incorrect recording of photographic images does not make it possible to determine the area of the lesion via software. This problem is tackled by providing precise instructions on the correct use of the tools available for the retrieval of images.

Discontinuity of patients can affect recovery times. Before recruiting a patient, the doctor ensures that the patient is available to go, with the required timing, to the clinic, for the scheduled visits. This fact is underlined several times when providing study information to the patient.

Interruption and withdrawal of subjects from the clinical trial

Patients who miss the visits for two consecutive weeks, before/until the 14th week, and the patients who miss the visits for one week, after the 14th week, will be reached by phone by the Principal Investigator to assess their availability to go on with the study; in the event that the patient does not intend to continue with the visits at the centre, they will be excluded from the study. Also, the patient who will turn out to be absent for more than half of the sessions will be excluded as well.

Following the resignation or withdrawal from the study by a patient, their data collection form will be identified, scanned and archived.

If a patient withdraws from the study, the Principal Investigator or his delegate records the event in the Patient Identification Register and on the Data Collection Form and stores all documentation.

Monitoring plan of the clinical investigation

To guarantee the conformity with ICH/GCP guidelines, the Clinical Research Coordinator (CRC) will be responsible for the study to be carried out in full observance of the Standard Operating Procedures, of the Protocol and other written instructions.

The main responsibilities of the CRC are to ensure adherence to the Protocol, to make sure that the data are accurately and fully registered and reported and to verify that the Informed Consent was obtained and registered for each subject before the beginning of the study.

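### The primary endpoint is measured from photographs in a trial that is open in practice, and the plan does not mask the measurement

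*Combined protocol and SAP*

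**What the plan says.** The Objectives section states: "The primary endpoint of the study is the percentage/rate of lesion area reduction". The Primary endpoint section sets the comparison at week 16.

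The Image Acquisition section describes how area is obtained: "The image analysis is made through an appropriate analysis algorithm that measures the area of the lesion", in mm². Areas are quantified "at the beginning, in the middle and at the end of the treatment". The section on factors that may impair outcomes confirms the dependence on the pictures: "An incorrect recording of photographic images does not make it possible to determine the area of the lesion via software".

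On identification, Image Acquisition requires: "The ruler with patient's ID code and date must appear in every picture". It and the section on registration of clinical data both add: "Each picture will be named with the patient code and the date of the visit". The Data Collection Form is issued already filled in with the recruitment code and the group.

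The Bias section covers staff training and concealment of allocation. The randomization grid is withheld from investigators. Folders show the patient ID on the outside, and inside "a label is placed with the assignment of the patient to one of the two groups". A sponsor officer signs the seal. The section says nothing about measurement.

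The Study design section mentions neither blinding nor a sham. Measurable parameters gives 32 visits in one arm and 16 in the other.

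**The concern.** Patients and treating staff know the arm, so the measurement is the one step of the primary endpoint that could still be masked. The plan does not mask it. The code visible in each picture is the key that joins the picture to the arm on the form and in the folder.

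The plan also leaves open whether the software finds the wound border unaided or whether a person traces or accepts it, sets the scale from the ruler, or joins several pictures of a wide lesion. If any of these steps needs judgement, a reader who knows the arm may measure slightly differently in one group. Such a shift enters the mean difference directly. A larger sample does not reduce it, and regression adjustment for confounders does not address it.

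**Working it through.** **1. The plan's own figure, for scale.** Inputs from Calculation of the sample size: 50% reduction in controls, a difference of 20% (read as 20 points, so 70% in the experimental arm), SD equal to 50% of each mean (25 and 35), two-sided α 0.05, power 0.80.

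- Pooled SD = √[(25² + 35²)/2] = 30.4.
- n per arm = 2 × (1.960 + 0.842)² × 30.4² / 20² = 36.3, so 37. With the t distribution it is 38.
- At 40 per arm, power is about 83%. The plan's statement that 80 patients suffice is correct on this reading.
- Read as a relative difference (10 points), 20% would need about 99-121 per arm. The 20-point reading is therefore the one that fits 80 patients.

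**2. Effect of a border shift.** Assumptions, not in the documents: a circular lesion, and a border drawn s = 0.05 or 0.1 cm further out in one arm at week 16 only. With baseline area A0 and reduction r, the week-16 area is A16 = (1 − r)A0 and the perimeter is P = 2√(πA16). The shift in percent reduction is about 100 × P × s / A0.

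| A0 (cm²) | r | A16 (cm²) | P (cm) | s = 0.05 cm | s = 0.1 cm |
|---|---|---|---|---|---|
| 2 | 50% | 1.0 | 3.54 | 8.9 | 17.7 |
| 2 | 70% | 0.6 | 2.75 | 6.9 | 13.7 |
| 10 | 50% | 5 | 7.93 | 4.0 | 7.9 |
| 10 | 70% | 3 | 6.14 | 3.1 | 6.1 |
| 50 | 50% | 25 | 17.72 | 1.8 | 3.5 |
| 50 | 70% | 15 | 13.73 | 1.4 | 2.7 |
| 100 (eligibility limit) | 50% | 50 | 25.07 | 1.3 | 2.5 |
| 100 (eligibility limit) | 70% | 30 | 19.42 | 1.0 | 1.9 |

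The last two columns are percentage points. A wider border lowers the measured reduction in the arm where it occurs.

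**3. The same habit at baseline too.** With radii r0 and r16, the measured reduction becomes 1 − [(r16 + s)/(r0 + s)]². For 10 cm² reduced by 70%, r0 = 1.784 and r16 = 0.977 cm. With s = 0.1, the ratio squared is (1.077/1.884)² = 0.327, so the reduction reads 67.3% and the shift is 2.7 points. Over r = 50-70% and both values of s, the shift is 1.1-2.7 points at 10 cm² and 2.5-5.8 points at 2 cm².

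**4. Consequence for the test.** Suppose there is no true difference, 40 patients per arm, SD 30.4, and an average shift b across one arm. The noncentrality is b / (30.4 × √(2/40)) = b/6.80 on 78 degrees of freedom. The two-sided type I error rises from 5% to 7.2% for b = 3, 11.2% for b = 5 and 21.3% for b = 8. For b = 5 it is 14.3% if the SD is 25 and 9.7% if it is 35. These values of b are illustrations.

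**The case against.** The strongest reply is that measurement by software, a ruler in every frame, framing rules and joint training already limit discretion, and that a code on a photograph is ordinary traceability. This is fair. If the software is fully automatic, little room for reader bias remains. The plan does not say that it is, and it provides for wide lesions to be pictured in several frames.

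Some stronger readings are tempting, but the documents do not support them:

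- A reader might infer that the dates give away the arm. Only three time points are measured, and their dates would look much the same in both arms. The weekly or twice-weekly pattern shows only to someone who sees the full series of photographs, and the plan does not say whether the image reader does.
- A reader might infer that the code shows the arm, or that the sponsor holds the code-to-arm list. The code is a centre digit plus a sequence number. Sponsor custody is an inference from the sealed folders described in the Bias section; no custodian of the grid is named.
- A reader might infer that borders are traced by hand. Manual input is possible but not described.
- A reader might infer that the bias could never be undone. The pictures are kept after the trial, so a later masked re-reading could detect and correct it. Statistical adjustment alone could not.
- The 18-point figure is the extreme of the calculation: a small lesion, a 1 mm shift, and one arm at one time point. Larger lesions shift less, and a healed lesion has no border to shift.

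**Conclusion.** The point holds as a gap in protection, not as evidence that bias will occur. Followed as written, the plan leaves the primary measurement unmasked in a trial whose arms are visibly different. It does not state who reads the images or how automatic the reading is.

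Under the stated assumptions, the possible shift runs from about 1 point for large lesions to about 18 points for a 2 cm² lesion, against a planned 20 points. The documents give neither a lesion-size distribution nor a reader-error figure, so the average shift over an arm cannot be estimated. It would be zero if the reading is fully automatic or the reader does not know the arm. The change is worth making because it is cheap and protects the primary result. It does not affect the sample size or the test.

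**What to change.** Add to Image Acquisition, with a cross-reference in Bias:

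- Original pictures keep code and date for traceability.
- Before measurement, existing study staff other than the reader, or a script, make copies under a random number, with code and date covered and the scale left visible. Pictures belonging to one wide lesion stay together.
- The planned reader measures the copies in random order across patients and time points, without access to the full photo series, the Data Collection Forms or the randomization grid.

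The same text should say who reads the images and which steps of the software, if any, need manual input.

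The cost is data-handling time for at least 80 × 3 = 240 images, and more where wide lesions need several pictures. No extra patient, visit or assessor is needed.

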As further detailed in the section on statistical analysis, it is expected to register, during the time of observation, a difference in efficacy between EmoLED protocol group ("Group 2") and SOC protocol group ("Group 1"), in terms of "healing rate", intended as a reduction of the wound area, but also as a progress, in a broad sense, of the overall clinical situation of the lesion, in terms of pain and quality of life.

Endpoint

Primary endpoint of the study

The primary endpoint will be the outcomes comparison in terms of healing rate of lesions treated with SOC only versus lesions treated with EmoLED and SOC, on week 16th.

L.U.C.E. Study Protocol version 3.0 (24/02/2020)

Secondary endpoint

- 1) Safety of treatment
- 2) Evaluation of the healing time of the lesions treated with the standard method (Group 1) versus the lesions treated with the EmoLED Protocol (group 2);
- Evaluation of the treatment of chronic ulcers in patients undergoing standard treatment versus EmoLED treatment about life quality (QoL) in 16 weeks, through generic questionnaires as the EuroQiL-5D2 and specific questionnaires as the Wound-Qol3;
- 4) Evaluation of costs related to the treatment and control group, in both the NHS and society perspective
- 5) Evaluation of VAS scale in both groups;
- 6) Evaluation of satisfaction, complexity and helpfulness of EmoLED device, considering both the perspective of patients, and the one of doctors and health care workers involved;
- 7) Evaluation of cost-effectiveness using EmoLED for the treatment of ulcers.

Measurable parameters

The key data and lesion's pictures of each patient will be collected in the Data Collection Form, after the enrollment and the signature of the Informed Consent:

- Group 1: V1 (Visit 1 and first treatment), V2, V3, V4... until V32 (32 treatments are planned during 16 weeks, 2 per week)
- Group 2: V1 (Visit 1 and first treatment), V2, V3, V4... until V16 (16 treatments are planned during 16 weeks, 1 per week)

The parameters used to define the study result will be found through:

- Photographic images of lesions treated with EmoLED and control lesions
- Data Collection Form filled by the medical staff during the visit
- Economic/organizational impact survey
- Medical/clinical/social impact survey
- Survey on the usability of the device
- Detection of pain through VAS scale

Registration of clinical data

The data related to the evaluation of the study endpoints are acquired, for both groups, during the visits.

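### Baseline quality of life and the first-visit cost questionnaire are recorded on a form that shows the patient's group, so staff know the arm before the baseline is taken

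*Combined protocol and SAP*

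**What the plan says.** Four parts of the protocol have to be read together.

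- **Bias.** The randomisation grid is withheld from investigators. Instead, "paper folders are distributed containing the data collection forms". The patient ID is outside, and "on the inside a label is placed with the assignment of the patient to one of the two groups". On the seal: "These folders are closed through an adhesive label", which bears a sponsor signature.
- **Data Collection Form.** "The Data Collection Form is unique for each patient and includes: Clinical Section, Quality Life Section and Economic Section". The group is on the form as well as on the label: "The Data Collection Form is already completed with the patient's recruitment code and the group they belong to". On timing: "The quality section survey will be administered on the first and last visits, and also every 4 weeks". The cost questionnaires are given to patient and caregiver at the first visit, which then serves as the reference for adherence-related costs.
- **Measurable parameters.** Key data and pictures are "collected in the Data Collection Form, after the enrollment and the signature of the Informed Consent". Visit 1 is also the first treatment in both groups, so there is no separate baseline visit.
- **Statistical analysis.** Quality of life is compared between groups by t-test at baseline, at 16 weeks and as the change between the two.

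Eligibility is handled elsewhere. Under Enrollment point, the criteria are checked and entered in an Enrollment Registry before the patient counts as enrolled.

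**The concern.** The sealed folder protects assignment, but it also holds the paper on which the baseline is recorded. Reaching the form reveals the group twice, on the inner label and on the form.

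The arms differ visibly: two visits a week, or one visit a week plus the lamp. No blinding is described. Patient-reported scores are the data most open to knowledge of the arm, through the patient's own expectation or the way staff put the questions.

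A baseline taken under that knowledge may itself be affected by allocation. A between-group difference at baseline could then no longer be read as chance imbalance, and subtracting the baseline could bring a bias into the change score. Analysis afterwards could not recover the unaffected value.

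**Working it through.** The plan states no figure on this point. The check is one of sequence, followed by simple algebra.

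**Step 1: the order of events.** Consent is signed. Eligibility is checked and entered in the Enrollment Registry. The folder is opened to reach the form. Visit 1 data are recorded and the first treatment is given. No section places the first-visit questionnaires before the opening, and none describes a baseline page kept outside the folder.

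**Step 2: which items are exposed.**

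| Item | Where recorded | Position relative to opening |
|---|---|---|
| Aetiology, chronicity, lesion size | Assessed for eligibility | Assessed before the folder is needed; later copying onto the form is not a new measurement |
| First-visit EQ-5D, Wound-QoL | Quality-of-life section of the form | After opening, as written |
| First-visit cost questionnaire | Economic section of the form | After opening, as written |
| First pain VAS | Asked at each visit | No order set |
| First photograph | Digital; needs only patient ID and date | No order set |
| Marking of the index lesion | On the skin; widest-area rule | No order set |

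**Step 3: what a shift does to each planned comparison.** Define each term as EmoLED minus control, scored so that higher is better. Let T be the true week-16 effect, S0 the baseline shift caused by knowing the arm, and S16 the week-16 shift from the same cause.

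- Baseline comparison: S0, where randomisation should give 0 on average.
- Week-16 comparison: T + S16. S0 does not enter.
- Change from baseline: (T + S16) − S0, so the bias is S16 − S0.
- Regression adjusted for baseline with within-arm slope b: T + S16 − b·S0. The plan names regression models against confounding but does not list baseline as a covariate.

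Relief at baseline in the EmoLED arm makes S0 positive. If S16 = 0, the bias in change is −S0, which hides a benefit. If S16 = S0, the two cancel in the change score. The sign is therefore unknown.

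**Step 4: illustration on assumed values.** Take 40 per arm (Number of patients expected to enroll), a two-sided t-test at 5% and T = 0. Let d be the size of S16 − S0 in SDs of the change score. The noncentrality is d × √(40/2) = 4.47d.

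| Assumed d | Noncentrality | Rejection rate |
|---|---|---|
| 0 | 0 | 5% |
| 0.1 | 0.447 | 7.3% |
| 0.2 | 0.894 | 14.3% |
| 0.3 | 1.342 | 26.3% |

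The values of d are assumptions. Nothing in the documents indicates which, if any, applies.

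**The case against.** **A reader might infer that nothing can be measured before the folder is opened, or that concealment fails.** The documents do not support either. Eligibility is settled first in a separate registry, and the form comes into use only after enrolment. Allocation stays concealed up to that point.

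**A reader might infer that the primary endpoint is compromised.** That goes too far. Photographs are digital and need only the ID printed outside the folder. Area comes from an image algorithm with a ruler in frame, and the index lesion follows a fixed widest-area rule. If a different lesion were chosen, its final area would be measured too, so inflating the baseline area alone does not describe that case. The risk is small and conditional on the order a site happens to follow.

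**A reader might infer a biased pain result.** The plan evaluates VAS in both groups but specifies no test of change in VAS, so no planned comparison is shown to be affected.

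**A baseline shift need not pass in full into the change score.** This is right. Patients live with their schedule throughout, so S16 may offset or exceed S0.

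**The cost questionnaire is not a pure baseline.** This is also right. It is meant to capture resource use under the two approaches, and costs are compared by Mann-Whitney test, not as change. Its exposure lies in its use as a first-visit reference.

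**When the patient learns the group is not stated.** Patient knowledge at baseline is therefore an inference. Staff knowledge follows from the folder for whoever opens it or handles the form.

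These objections narrow the point. They leave untouched the location of the quality-of-life section and the two planned tests that use its first-visit value.

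**Conclusion.** The point holds for first-visit quality of life and, to a lesser degree, for the cost questionnaire. Followed as written, the protocol has staff collect both knowing the arm. Two of the three planned quality-of-life comparisons, at baseline and in change, depend on that measurement. The week-16 comparison does not.

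The bias in the change score is S16 − S0. Its size cannot be derived from the documents and its direction is unknown. The rejection rates of 7.3% to 26.3% illustrate assumed net shifts of 0.1 to 0.3 SD; they are not estimates. The conclusion rests on two readings: that the quality-of-life and economic sections are physically part of the form in the folder, as the text says, and that sites follow the text. A site might ask the questions first and open later, but nothing requires or documents this.

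The matter concerns secondary endpoints. It should be corrected because the correction is cheap and the lost baseline cannot be rebuilt.

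**What to change.** Put the baseline EQ-5D, Wound-QoL, first VAS and cost questionnaire on pages without a group mark, attached outside the sealed folder under the patient ID. Add to the Data Collection Form and Bias sections:

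*The index lesion is marked, the baseline photograph taken and the baseline questionnaires completed and dated before the folder is opened; the date and time of opening are recorded.*

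This makes S0 zero by design. It does not remove S16: open-label reporting at week 16 remains and would then affect the change and week-16 comparisons equally. That is easier to interpret than a difference of two unknown shifts.

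**Cost.** No extra visit or staff. The baseline pages must be separated from the form, whose second part is a matrix with observation times as columns, so the first VAS needs its own page. Folders for 80 patients must be re-packed, and the step before allocation is known becomes slightly longer. If the study is already approved, a protocol amendment is needed. The protocol suspends the trial while a substantive amendment awaits ethics approval, so the change is best made before recruitment starts.
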